Rahman, & Datta, 2012) and animal studies (Bikson et al., 2004; Rahman et al., 2013) have shown that the effects of tDCS may result from subtle changes in neuronal membrane polarization that can affect cells' probability of firing. This effect can be modified pharmacologically (Nitsche et al., 2003), with dopamine agonists such as L-dopa increasing the effect (Kuo, Paulus, & Nitsche, 2008) while dopamine antagonists (sulpiride) reduce it. The effects of tDCS on motor learning may be mediated by its impact on brain-derived neurotrophic growth factor (Fritsch et al., 2010).

[figure not shown]
Safety of tDCS. tDCS is generally considered safe, based on data from multiple studies (Bikson, Datta, & Elwassif, 2009). A recent systematic review completed by the FDA of the safety of iontophoresis devices found 25 studies using iontophoresis devices for a variety of indications (available for download on the FDA website). The FDA staff review concluded that while incidence of adverse events varied widely among studies, "most adverse events were mild and did not require treatment. These studies support the safety of iontophoresis devices for these indications." [pg. 37]. Another review of adverse events during multiple studies of tDCS with 102 patients and 567 tDCS sessions (Poreisz, Boros, Antal, & Paulus, 2007) showed that the most common effects of tDCS were "tingling," "itching sensation," "burning sensation," "pain," "headache," and "fatigue." The frequency of these effects varied widely across studies reviewed but no serious events, such as burns, were reported.

A recent study of tDCS for depression (Brunoni et al., 2013) that used the same device to be used in the proposed study (Chattanooga Lonto), reports safety data for 103 patients. In this study, only the adverse effect of skin redness was more common in the active treatment group than in the sham tDCS group. No change in cognitive function was seen across groups, but several patients developed hypomania and 2 manic episodes occurred (there were similar occurrences of hypomania or mania across treatment groups of sertraline, tDCS, or their combination).

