Participants who continue to meet all study criteria with respect to medical history and medication use (see flow sheet) will complete four brief neuropsychological measures (Hopkins Verbal Learning Test; Trail Making Test Parts A and B; Wechsler Adult Intelligence Scale Digit Span subtest; Grooved Pegboard; all listed below) as well as complete the Center for Epidemiological Studies Depression and the Patient's Own Assessment of Functioning Scale. These will take approximately 45 minutes to complete. After completing these measures, they will be provided with a break (approximately 5-10 minutes) while the researcher scores the measures and determines the potential participant's eligibility given the evidence of both subjective cognitive complaints and objectively below average (at least 1 standard deviation below normative performance) on at least two of the measures. If participants are not eligible based on their cognitive performance, they will be thanked for their attendance, asked if they have any questions, and provided compensation.

Participants who show evidence of below average cognitive performance in two areas assessed will be informed that they are eligible to participate in the study. Their continued interest in participation will again be elicited, and if they continue to state they would like to participate, the investigator will review the written informed consent form with the potential participant, answer questions about the study, and provide the potential participant with sufficient time to review the written informed consent form. The investigator will then ask the participant to briefly recount the purpose of the study as well as its risks and benefits using a previously validated procedure

(Palmer et al., 2005). If participants cannot provide adequate answers to these questions, the person obtaining informed consent will review the material until they achieve a satisfactory performance defined as a score of 4 out of a possible 6 on the three questions (see visit flow sheet for questions and scoring criteria).

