Participants receiving **active tDCS** will then receive 1.5 mA tDCS delivered by the Chattanooga Ionto electrophoresis device for 20 minutes while completing working memory training with the Brain Workshop software (example computer screens are included in the Appendix). The device provides an initial 30 s ramp-up of current so as to minimize discomfort and is designed to deliver a constant current even in the face of possible fluctuations in impedance due to changes in electrode or skin characteristics (e.g., increased resistance as the electrode dries). It includes circuitry that continuously monitors impedance so that if it changes beyond safety parameters the device immediately shut off with an audio alarm. This provision reduces risk of participant discomfort or other negative effects. The device also is controlled with a timer that guarantees a specific dose tDCS; it automatically ramps down the current and shuts off at the end of the session (20 minutes).

Participants receiving **sham tDCS** will be treated in the same fashion (fitted with the electrodes and headband) but current will be provided only for the 30 sec ramp up period and five seconds after that, when the current will ramp down. This provides no tDCS-related effect but provides the participant with a stimulus that is discernible by most persons. Since many persons only perceive the current at the beginning of a stimulation session (even when it continues for 20 minutes) this is believed to be an adequate control and is a strategy has been used in multiple other studies.

As the device does not provide for double-blinding in the delivery of tDCS (i.e., the operator must program it and will know if the person receives active or sham stimulation), [name] will plan

to sit to one side and behind the participant in order to monitor the participant, encourage his work on the cognitive training task, provide tutoring on the task and interacting with the computer as needed. The study is thus single blind, and we will assess the success of blinding by asking participants which group they were in as part of the final study visit.

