Cognitive Training. During the study visit, both groups will be asked to work with the n-back training program Brain Workshop. The phrase “n-back” refers to the task’s requirement to monitor a series of discrete events (either blue blocks flashing on the screen in one of 9 positions or a series of letter heard over audio) and remember one that occurred a specific number prior to the current one. The number of prior events monitored is the “n.” The participant is asked to press a letter on a keyboard when the current stimulus matches one delivered “n” times previously. For example, for a 2-back task using the letter series “a – d – g – d,” the participant would respond with a key press when hearing the second letter “d” as it matches a letter presented two instances before the current one.

As this task can be challenging for those with cognitive impairments and we have previous experience in using it with older persons, the task’s difficulty is tailored to individuals’ abilities and can be increased as the participant shows greater levels of performance over time. Participants’ performance is tracked automatically by the software and will be recorded only with the participant’s research number.

At the conclusion of this visit and all subsequent visits, participants will provide brief ratings of their cognitive function, mood, and level of discomfort (see Appendix for questions).

Randomization: Participants will be randomized to treatment condition in permuted blocks of four, with a plan to recruit six blocks of four (total participants 24) based on power analyses that suggest a sample size of 12 in each group provides a power of 0.80 to detect between group differences. As we wish to obtain a final sample size of 12 in each group, however, depending on drop outs or persons otherwise lost to follow-up, we will plan to recruit two additional blocks of 4 up to a total number of 32 participants. The planned enrollment table in section 2A of this protocol thus indicates a possible total enrollment of 32.

5) Subsequent study visits. Participants will complete a total of six 20-minute training sessions with sham or true tDCS and working memory training. Participants will be asked to complete three sessions per week, and must complete all training sessions within three weeks.

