6) Final study visit. At the final study visit, participants will complete the same brief neuropsychological battery done at the screening visit, the depression rating scale (CES-D), the Patient’s Own Assessment of Functioning Scale, and be asked to state whether they were in the active or sham experimental groups. Final open-ended questions will elicit participants’ experience with the study and whether they found it useful (see final visit flow sheet in Appendix).

Part 4 – Sources of Data Information

Are you using questionnaires, tests, instruments, or forms?

Yes	No
	

If "Yes", list them below and include a copy of each as appendices.

Telephone screening script
Eligibility visit flow sheet with script and data recording sheet
Trail Making Test
Hopkins Verbal Learning Test
Grooved Pegboard
Wechsler Adult Intelligence Scale Digit Span recording sheet
Center for Epidemiological Studies – Depression scale (CES-D)
Patient's Own Assessment of Functioning (POAF)
Participant study visit log (documents date and time of visit)
Final visit flow sheet

Do you plan to use any data from records or archives?

Yes	No
	

If "Yes", please describe (such as data originally created for non-research purposes or data created as a result of a previous study).

HIV RNA viral load and CD4 count from patient's personal records; potential eligibility for participants from a previous study will be evaluated using self-report of cognitive difficulties and performance on cognitive measures ("Improving Health Literacy about HIV Infection: Phase I & II;" NSU IRB Protocol No. 06120904Exp).

Do you plan to use any de-identified data?

Yes	No
	

If "Yes", please describe the data and how it will be de-identified.

N/A

3. Additional Study Information

3.A. Clinical Testing

Food and Drug Administration Investigational Drugs and Devices

Does the study involve the use of an investigational drug?

Yes	No
	

If "Yes", has an Investigational New Drug application been submitted for the drug?

Yes	No
	

Does the study involve the use of an investigational device?

Yes	No
	

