Risk Minimization	Participants will be closely monitored during treatment sessions. If impedance changes during treatment, the tDCS device will automatically stop current delivery. Participants will be encouraged to report any discomfort, and should the discomfort increase substantially the tDCS delivery will be stopped. If the person experiences vesicles or evidence of skin irritation that does not resolve promptly (i.e., within 20 minutes) after discontinuation of the tDCS, he or she will be dropped from the study.

Risk/Discomfort	Burn at electrode site
Likelihood	Very low (less than 1%)
Magnitude/Duration	Moderate/throughout the study
Risk Minimization	Participants will be closely monitored during treatment sessions. If impedance changes during treatment, the tDCS device will automatically stop current delivery. [name] or [name] will be in the office at all times during study visits, and will be able to monitor the participant. Participants will be encouraged to report any discomfort, and should the discomfort increase substantially the tDCS delivery will be stopped. A recent FDA advisory panel reviewed adverse effect data from studies using electrophoresis devices and concluded that risks of burns are low (see discussion of safety, above).

Risk/Discomfort	Fatigue
Likelihood	High (35% based on data from Poreisz et al., 2007)

Magnitude/Duration	Moderate/throughout the study
Risk Minimization	Participants will be closely monitored during all study visits; each visits will begin with a review of any problems that occur between visits and each will end with a review of discomfort and an open-ended discussion of any problems of concerns so that participants can readily communicate any issue they experience.
Risk/Discomfort	Difficulties in concentrating
Likelihood	Moderate (4-10% based on data from Poreisz et al., 2007)
Magnitude/Duration	Moderate/throughout the study
Risk Minimization	Participants will be closely monitored during all study visits; each visits will begin with a review of any problems that occur between visits and each will end with a review of discomfort and an open-ended discussion of any problems of concerns so that participants can readily communicate any issue they experience.
Risk/Discomfort	Manic or hypomanic episode
Likelihood	Low
Magnitude/Duration	Moderate/throughout the study

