Cognitive Training with and without tDCS to Improve Cognition in HIV

December 2, 2014

Statistical Analysis Plan

Study outcomes will be evaluated through analysis of group differences on neuropsychological measures after correction for baseline differences in age, disease status (CD4 count), mood, and baseline performance. Additional outcomes will include the rate of learning in the computer-delivered memory and attention task between groups. Individual and group slopes for the task will be plotted and visually inspected as well as tested using parametric statistics.

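### Minor: a participant dropped for a persistent skin reaction has no planned outcome assessment; the likely bias is small, and keeping the outcome is cheap

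*Protocol*

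**What the plan says.** Protocol Section 3.K (risk minimization for skin discomfort) covers vesicles and irritation that has not settled within 20 minutes: "after discontinuation of the tDCS, he or she will be dropped from the study". The wording ends study participation, not only stimulation.

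The outcome is measured twice. In Section 2.C Part 3, step 3, candidates "will complete four brief neuropsychological measures" at the eligibility visit. In step 6, "At the final study visit, participants will complete the same brief neuropsychological battery done at the screening visit". The supplied text describes no other post-baseline battery and no assessment for people who leave early.

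On attrition, the Randomization paragraph of Section 2.C says that "depending on drop outs or persons otherwise lost to follow-up, we will plan to recruit two additional blocks of 4", with a ceiling of 32. The aim is 12 final participants per group.

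Protocol Section 3.M and the SAP carry the same analysis text: group differences on the neuropsychological measures "after correction for baseline differences in age, disease status (CD4 count), mood, and baseline performance". Neither names an analysis set, a rule for withdrawn participants or a method for missing outcomes.

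**The concern.** Taken together, these provisions discard the outcomes of people already randomised, treated and tested at baseline, for a reason that arises from the study procedure. Extra blocks restore the count but not the missing outcomes. Each such loss is 1 of 12 (8%) of the target arm, or 1 of 14 (7%) once one extra block has been added.

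The loss could fall unequally. Active participants receive 20 minutes of current. For sham, "current will be provided only for the 30 sec ramp up period and five seconds after that", before ramp-down. The protocol's safety summary adds that skin redness was more common on active than on sham in the cited depression study using the same device. If losses differ by arm and relate to outcome beyond what the baseline adjustment removes, the comparison is biased. The direction favours active if those lost would have scored worse, and reverses if they would have scored better.

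The gap is not specific to skin reactions: it applies equally to voluntary withdrawal, missed sessions and loss to follow-up. The learning-rate outcome is only partly affected, because n-back performance is recorded during each training session.

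**Working it through.** **The plan's own figures.** The stated power of 0.80 with 12 per group cannot be reproduced, because no effect size, alpha or outcome is given. Assuming two-sided alpha 0.05 and an unadjusted t test, it corresponds to a difference of about 1.20 SD. The ceiling of 32 allows for 25% loss: 24 / (1 − 0.25) = 32.

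**How many are randomised if one or two are lost.** Starting from 12 per arm, two active losses leave 10. One extra block of four adds two per arm, giving 14 randomised and 12 active participants with outcomes. The relevant case is therefore 14 per arm, not 16.

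**How likely a loss is.** The documents give no rate, so the rates q below are assumptions. P(at least one) = 1 − (1 − q)^n, for n = 12 and n = 16 active participants:
- q = 1%: 11% and 15%
- q = 5%: 46% and 56%
- q = 10%: 72% and 81%

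**Bias in the adjusted comparison.** Assume no true effect and loss in the active arm only. Approximately,

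bias = λ(p) × (r − ρ·r_B), with λ(p) = φ(z_p) / (1 − p).

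Here p is the fraction lost, r and r_B are the correlations of the tendency to be lost with outcome and with baseline, and ρ is the baseline-outcome correlation. Assumed values are r = 0.5 and ρ = 0.5 to 0.7. The lower ρ is included because inclusion criterion 6 restricts the range of baseline scores.

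- One of 14 lost: p = 0.071, λ = 0.1364 / 0.9286 = 0.147
- Two of 14 lost: p = 0.143, λ = 0.2256 / 0.8571 = 0.263

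| Lost | Loss related equally to baseline and outcome (r_B = 0.5) | Loss unrelated to baseline (r_B = 0) |
|---|---|---|
| 1 of 14 | 0.147 × 0.15 = 0.022 (ρ = 0.7); 0.147 × 0.25 = 0.037 (ρ = 0.5) | 0.147 × 0.5 = 0.073 |
| 2 of 14 | 0.263 × 0.15 = 0.039 (ρ = 0.7); 0.263 × 0.25 = 0.066 (ρ = 0.5) | 0.263 × 0.5 = 0.132 |

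Simulation of the planned covariate-adjusted analysis agrees closely. The formula slightly overstates the largest entry, which simulates at about 0.12. The ranges are therefore 0.02 to 0.07 SD and 0.07 to 0.12 SD, with type I error of about 5% to 7.5%.

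**When there is no bias.** If loss is unrelated to outcome, r = r_B = 0 and the bias is zero. If loss acts only through baseline, r = ρ·r_B (for example 0.5 = 0.7 × 0.714) and the bias is again zero.

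**What retention costs in sensitivity.** If 2 of 14 active participants get half or none of the benefit, the estimated effect shrinks by 0.5 × 2/14 = 7% or 2/14 = 14%. For 2 of 16 it shrinks by 6% or 13%. As an illustration at ρ = 0.7 with four covariates, the 80% detectable difference is 0.763 SD for completers of 14 versus 16, and 0.735 SD for 16 versus 16. Allowing for dilution, the full-treatment effect needed with everyone analysed is 0.735 / 0.9375 = 0.784 or 0.735 / 0.875 = 0.840 SD. Retention therefore brings no power gain.

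**The case against.** The strongest reply is that the event may never occur and would matter little if it did. Section 3.K puts burns below 1%, the regulatory review quoted in Section 2.C says "most adverse events were mild and did not require treatment", and people with a sensitive scalp are excluded. No link between skin reaction and cognition is shown. Analysing partly treated people may also cost more than it recovers: a dilution of 7% to 14% is of the same order as the bias removed. For a pilot meant to show feasibility and potential efficacy, which question to answer is a design choice. This largely stands, and it is why the point is minor. What it does not answer is that the plan makes the choice by silence and never collects the data that would let either question be answered.

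A reader might infer three stronger claims, and the documents support none of them.

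- **That over 20% of active participants would be dropped.** The figure above 20% in Section 3.K covers any discomfort, tingling, itching or redness, not the persistent reaction that triggers exit.
- **That higher loss on active is established.** The exposure difference and the redness finding make it plausible, but redness is not the trigger.
- **That a completers-only analysis is prescribed.** No such statement appears; the exclusion follows from a missing outcome and an unnamed analysis set.

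A provision for withdrawn participants could also sit in material not available for review: the final visit flow sheet, the consent pages, or the pages removed after heading 3.Q. The point is limited to the supplied text.

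**Conclusion.** The gap is real and minor. On the supplied text, someone dropped under the skin-reaction rule, or lost for any other reason before the final visit, contributes no neuropsychological outcome, and nothing says how the analysis treats that person.

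For one or two active losses at 14 per arm, the bias is 0.02 to 0.07 SD, or 0.07 to 0.12 SD in the upper case. These figures rest on an assumed loss-outcome correlation of 0.5, a baseline-outcome correlation of 0.5 to 0.7 and no sham losses. Weaker correlation or similar loss in both arms would reduce the bias towards zero. The documents supply none of these inputs. They do not support a claim that this rule threatens the trial's conclusion. The case for change is an avoidable loss of outcomes that is cheap to prevent.

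**What to change.** Leave the rule for stopping stimulation unchanged.

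- **Section 3.K:** reword so that stopping stimulation does not end outcome follow-up.
- **Section 2.C:** invite every randomised participant who still consents to the final visit, whatever the number of sessions completed. Fix the time from the first session, identically in both arms; the end of the existing three-week training window would serve. A fixed time is needed because the visit is now placed only after the six sessions and is undefined for someone who stops early.
- **Section 3.M and the SAP:** analyse all randomised participants with outcome data in their assigned arm, including any extra blocks, with the planned covariates. Report losses by arm and reason, and give completers as a sensitivity analysis.
- **Those who do not return:** show how the estimate moves if each missing outcome lies 0.5 or 1 SD above or below its predicted value. Per person this is 0.5/14 = 0.04 or 1/14 = 0.07 SD at 14 per arm, and 0.03 or 0.06 SD at 16.

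This also covers dropout for every other reason. The cost is wording in the Protocol and SAP and a few extra final visits at the $40 rate in Section 3.D; step 6 lists no stimulation at that visit. The downside is the 7% to 14% dilution shown above, and some people will not return. No power gain is claimed.

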Cognitive Training with and without tDCS to Improve Cognition in HIV

December 2, 2014

Statistical Analysis Plan

Study outcomes will be evaluated through analysis of group differences on neuropsychological measures after correction for baseline differences in age, disease status (CD4 count), mood, and baseline performance. Additional outcomes will include the rate of learning in the computer-delivered memory and attention task between groups. Individual and group slopes for the task will be plotted and visually inspected as well as tested using parametric statistics.
